We will evaluate the impact of DHP's quality improvement pilot program (called, *Nurture*), which included nutrition education and food support offered to a subset of pregnant women aged 30 years and above and were covered by the Medicaid Managed

Care Organization (MCO) plan in their “STAR” and “CHIP” programs during October 2022 and July 2023.

From this population, DHP randomly selected a subset of approximately 500 women during that period, from which approximately 200 were in the program, the “exposed group.” The women who were covered during the same period but were not selected were not exposed to the program and will compose the “comparison group.”

The objective is to compare maternal and neonatal outcomes between those who participated in the program (exposed group) and those who did not (comparison group).

Analysis Plan:

Claims data will be pulled retrospectively from the insurer's database and other administrative sources. Information will include healthcare utilization, maternal outcomes during pregnancy, and neonatal outcomes at and post-delivery. The primary analysis involves comparing the outcomes of the exposed group with the comparison group. Statistical methods appropriate for this type of administrative data will be employed to assess the differences between the two groups, adjusting for potential confounders.

The *Nurture* program’s impact will be evaluated using claims data received from DHP concerning two composite outcomes: adverse maternal health outcomes (Composite 1) and adverse neonatal outcomes (Composite 2), as shown in Table 1 below. In addition, we will explore single outcomes, such as delivery mode (vaginal vs c-section), cost data, and birthweight, adding nuance to our understanding of the program's impact.

We will primarily use logistic regressions to predict the primary, binary composite outcomes for mothers and newborns, adjusted for risk factors such as maternal age, gestational age at the time of enrollment, pre-existing diabetes, hypertension, and being overweight pre-pregnancy (shown in Table 2). The program “dose” variables are anticipated to be continuous predictors that include both ‘usual care’ (i.e., prenatal care visits) and *Nurture* program elements (the dollar value of the gift cards spent up to 30 days after stopping the program, total number of nutrition consult minutes); see Table 3.

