Because we expect cost data to be continuously distributed, linear regressions are expected to be more appropriate. The predictors will remain the same in all models irrespective of outcome, including the “dose” variables.

Table 1. Program outcomes from health claims

Composite outcome 1: Adverse health events during pregnancy	Composite outcome 2: Adverse health events at birth and newborn-related	Exploratory outcomes:

 • Gestational Diabetes Mellitus • Excessive weight gain during pregnancy • Pregnancy-associated hypertension 	
 • Pre-term birth (<37 weeks) • Neonatal Intensive Care Unit (NICU) • Small for gestational age • Large for gestational age • Stillbirths 	
 • Emergency Department visits • Cost (outpatient, inpatient, pharmacy, total) • Delivery mode (vaginal, c-section) • Birthweight collected from hospitals

Table 2. Population descriptors and demographics from health claims

Demographics	Health history (dichotomous)

 • Age (years) • Ethnicity • Location (Nueces/Hidalgo) • Gestational age at enrollment • Gestational age at delivery 	
 • Family history of diabetes mellitus • Pre-pregnancy diabetes mellitus • Pre-pregnancy overweight/obesity • History of gestational diabetes • Chronic hypertension

Table 3. “Dose” variables from program implementation tracking and health claims

Nurture Program uptake	Care Received

 Gift card usage (dollar amount) Packages received (counts) Nutritional consults (duration) 	
 Prenatal visits (counts) Referral to Case Management (dichotomous)

DHP’s Nurture enrollment:

1. DHP receives daily new health plan enrollees from the TX State. Their data analytics team identified new pregnant members aged 30 or older in bi-weekly “cycles” and ran an algorithm to randomly select a list of names to be notified and contacted by DHP’s Community Health Workers (CHWs).
2. Notifications: Members on the roster to be called received an SMS text with a URL to an informational page, which was also mailed as a hard copy to the member’s address on file.
3. Welcome calls: DHP’s CHWs called up to 3 times on consecutive days to welcome the women to the *Nurture* program, explain what to expect, confirm address for mailing out the packages, and book two phone nutritional consultations.

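### Prenatal visit counts sit in every model although the outcomes can change them and cost probably includes them, so the programme estimate can be biased in either direction

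*Combined protocol and SAP*

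**What the plan says.** The Analysis Plan in Section 3 makes the contrast of exposed with comparison women the primary analysis. It uses logistic regression for the two composites and expects linear regression for cost. The dose "variables are anticipated to be continuous predictors that include both" usual care and programme elements, and usual care is explained as "i.e., prenatal care visits". The paragraph ends with the rule that "The predictors will remain the same in all models irrespective of outcome, including the" dose variables.

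Table 3, under Care Received, has two entries: "Prenatal visits (counts" and "Referral to Case Management (dichotomous" (each shown without its closing bracket). Table 1 puts gestational diabetes, excessive weight gain and pregnancy-associated hypertension in Composite 1. Composite 2 contains "Pre-term birth (<37 weeks", NICU admission, small and large for gestational age, and stillbirth. The exploratory outcomes include "Cost (outpatient, inpatient, pharmacy, total".

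Three things are not stated: the period over which visits are counted, any model without these terms, and a group indicator among the listed predictors. Section 15 gives 224 exposed women, out of 511 selected, and about 1200 comparison women.

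**The concern.** Gift-card dollars and consultation minutes measure uptake of Nurture. Prenatal visits do not. They are ordinary care, recorded in both groups, so they would act as adjusters in any exposed-versus-comparison model. They are also not fixed at baseline, and their relation to the outcome changes from model to model:

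- In Composite 1, a diagnosis of gestational diabetes or hypertension can lead to more visits and to referral.
- In Composite 2, preterm birth ends the period in which visits can occur.
- In the outpatient and total cost models, visits are probably part of the quantity being modelled.

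A single fixed predictor set cannot suit all three. At stake is whether the two primary composite results can be read as programme effects, and whether the cost models show what the programme does to spending on prenatal care.

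**Working it through.** The plan gives no figure for visits, so there is nothing of its own to reproduce. Table 4 is indexed only by event rates and does not bear on this point.

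**Inputs from the documents.** 224 exposed and about 1200 comparison women (Section 15); a 30% event rate, one of the two comparison rates in Section 16; alpha 0.05, taken as two-sided.

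**Assumed inputs.** b is the change in visits caused by the event, c is the extra visits of exposed women with the same outcome, and s = 3 is the visit SD within outcome and group.

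**Formula.** Let visits V be normal with mean a + bY + cG and SD s, where Y is the event and G the group. By Bayes' rule, logit P(Y=1 | G,V) equals logit P(Y=1 | G) plus the log ratio of the two visit densities. That log ratio is [2b(V − a − cG) − b²]/(2s²). Its group term is −bc/s², so adjusting for visits multiplies the programme odds ratio by exp(−bc/s²).

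**Results with no true effect.** Each row with a group difference was checked with 1,500 simulated data sets of 224 v 1200. Without visits in the model, 4% to 5% of tests rejected.

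| b | c | exp(−bc/s²) | Simulated OR | Rejection at 5% |
|---|---|---|---|---|
| +3 | 1 | exp(−3/9) = 0.72 | 0.72 | about 46% |
| +2 | 1 | exp(−2/9) = 0.80 | 0.79 | about 27% |
| +2 | 0.5 | exp(−1/9) = 0.89 | 0.89 | about 9% |
| −3 | 1 | exp(3/9) = 1.40 | 1.40 | about 47% |
| any | 0 | exp(0) = 1.00 | about 1.00 | about 5% |

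For scale, an odds ratio of 0.72 at 30% gives odds of 0.4286 × 0.7165 = 0.307, a rate of 0.307/1.307 = 23.5%. That is close to the 23% column of Table 4.

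**Composite 2 as a mixture.** The −3 row treats every event as preterm, but the other components need not shorten pregnancy. With one extra exposed visit, the average shift is the preterm share times −3:

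- One half preterm: shift −1.5, roughly exp(1.5/9) = 1.18; simulated 1.16, rejection about 16%.
- One third preterm: shift −1, roughly exp(1/9) = 1.12; simulated 1.10, rejection about 10%.
- One third preterm and the other events adding 1.5 visits: shift (1/3)(−3) + (2/3)(1.5) = 0; simulated 0.99, rejection about 5%.

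The formula is only approximate here, because visits among events are no longer normal with SD 3.

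**Cost.** Write cost as kV + R, with k the cost of a visit and R all other cost. If the groups differ by d visits, the total difference is kd plus the difference in R. When R is unrelated to V within group, the group coefficient adjusted for V keeps only the difference in R, and kd is lost. The documents give neither k nor d, so no dollar size can be stated.

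**The case against.** The strongest reply is that outcome-driven visits alone do not bias the logistic composites. That is right: with c = 0 the shift is zero. The bias needs a group difference in visits among women with the same outcome, and the documents do not show one. They make it plausible, because the exposed women answered calls and opted in while the comparison women passed no such filter.

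A second reply is that visits may mark care-seeking, so adjusting could reduce selection bias. This stands as a possibility but is unreliable. In a simulation where care-seeking raised participation and visits and lowered risk, with a true odds ratio of 1.00, the unadjusted estimate was 0.86. Adjusting for visits gave 0.77 when an event added three visits, 0.87 when it had no effect on visits and 1.02 when it removed three. Whether adjustment helps depends on the unknown effect of the outcome on visits.

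Other points also stand. The dose terms are only anticipated, and no group term is specified. The odds ratios above come from a simplified group-plus-visits model without the uptake terms or risk factors. Referral may not be intended: the text says continuous and names only visits, while Table 3 lists a yes/no referral. That visits fall within outpatient or total cost is a reasonable inference, not a statement in the documents.

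A reader might infer that the programme estimate is biased, and specifically that Nurture will look protective for mothers and harmful for newborns. The documents do not support that. They contain no visit data, the Composite 2 shift can vanish under a plausible mix of events, and nothing suggests that excessive weight gain, a Composite 1 component, adds visits.

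**Conclusion.** The point holds as a risk built into the written plan. A variable that accrues partly after enrolment, can be a consequence of the outcomes and is probably a component of cost is a predictor in every model. For the composites, bias requires a group difference in visits given the outcome; its sign and size are unknown. The illustrations run from no bias to odds ratios of 0.72 and 1.40, and rest on assumed values of b, c and s. For cost, adjustment removes whatever part of the programme's effect runs through prenatal care use, provided visits are counted in the cost category modelled. The primary composites are affected and the correction is cheap, so the plan should be changed before analysis.

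**What to change.** - In the exposed-versus-comparison models, name the group term and adjust only for covariates fixed at or before enrolment. The risk factors named in the Analysis Plan (age, gestational age at enrolment, pre-existing diabetes, hypertension, pre-pregnancy overweight) can serve, with hypertension read as the chronic hypertension of Table 2.
- Remove prenatal visit counts, and case-management referral if it was intended, from these models for both composites and all exploratory outcomes. Limit the same-predictors rule accordingly.
- Report visits and referral by group as process outcomes. Label any model containing them secondary and descriptive, and state its counting window.

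Counting only care before selection for the program is not a workable substitute adjuster. Comparison women were never on a roster and have no such date, and rosters were drawn from new plan members, who may have few earlier claims.

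The cost is a wording change with no new data. The primary models would no longer describe how usual care relates to outcomes, and they lose a possible but unreliable proxy for care-seeking. Removing visits does not itself deal with selection into the exposed group.

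### One predictor set for every outcome, with no number of fetuses or previous caesarean, leaves avoidable confounding: small for Composite 2, larger for delivery mode

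*Combined protocol and SAP*

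**What the plan says.** The Analysis Plan in section 3 specifies logistic regression for the two binary composites, "adjusted for risk factors such as maternal age, gestational age at the time of enrollment, pre-existing diabetes, hypertension, and being overweight pre-pregnancy", and refers the reader to Table 2. It also promises, in general terms, "adjusting for potential confounders". Linear regression is expected for cost. The plan then says "The predictors will remain the same in all models irrespective of outcome", and the same sentence extends this to the dose variables of Table 3.

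The rule therefore covers Composite 2 (pre-term birth, NICU, small or large for gestational age, stillbirth), which is a primary outcome. It also covers the exploratory outcomes, among them "Delivery mode (vaginal, c-section)", birthweight and cost.

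Table 2 lists age, ethnicity, location, gestational age at enrollment and at delivery, and five health-history items. One of these is "History of gestational diabetes". Number of fetuses and previous caesarean appear in none of Tables 1 to 3. Section 14 asks only for pregnancy and age 30 or over, so multiple pregnancies are not excluded. Section 15 gives 511 selected women, of whom 224 joined and 287 could not be reached, and a comparison group of about 1200 women who were not selected.

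**The concern.** A single predictor set suits all outcomes only if it contains the main baseline determinants of each. Here it holds none of the obstetric factors that bear most directly on some outcomes. A twin pregnancy is likely to be a Composite 2 event whatever the program does, and a woman with a previous caesarean is much more likely to have another. The sameness rule also prevents a predictor from being added only to the model where it matters.

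This would be a minor loss if the groups were balanced by design, but they are not. The selection was random, but the exposed group is the part of the selected list that could be reached by telephone and agreed to join, 224/511 = 43.8%. Women who are reached may differ from women who are not, and the comparison group has not passed through that filter. Balance has to come from the model. A difference in obstetric history could otherwise be reported as a program effect.

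**Working it through.** The plan states no figure that bears on this point, so there is none to reproduce. The prevalences and rates below are assumptions, shown as ranges. Group sizes (224 and 1200) come from section 15, and the 30% and 20% rates come from Table 4 in section 16.

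**1. Is the gap real under the most generous reading?** Suppose the open list admits every Table 2 item. History of gestational diabetes is then covered, but number of fetuses and previous caesarean still are not. Taking Table 2 whole would also bring in "Gestational age at delivery", which is measured after exposure and determines the pre-term component of Composite 2.

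**2. Confounding in Composite 2 from multiples.** With no program effect, the spurious risk difference is (imbalance in prevalence) × (r1 − r0), where r1 and r0 are the event rates with and without the factor.
- r1 = 70% to 85%, r0 = 28%: a 1-point imbalance gives 0.42 to 0.57 points.
- r1 = 70% to 90%, r0 = 30% to 35%: a 2-point imbalance (2% exposed v 4% comparison) gives 0.7 to 1.2 points, an odds ratio of 0.95 to 0.97.
- For scale, the standard error of the risk difference at a 30% rate is √[0.30 × 0.70 × (1/224 + 1/1200)] = 3.3 points.

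**3. Confounding in delivery mode from previous caesarean.** Same formula.

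| Previous caesarean, exposed v comparison | Caesarean rate with v without | Spurious difference | Spurious OR |
|---|---|---|---|
| 25% v 30% | 85% v 25% | 3.0 points | 0.88 |
| 25% v 30% | 90% v 20% | 3.5 points | 0.86 |
| 25% v 35% | 85% v 25% | 6.0 points | 0.78 |
| 25% v 35% | 90% v 20% | 7.0 points | 0.75 |

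With equal prevalence the spurious odds ratio is 1.00. At 30% prevalence, chance alone gives a standard error of 3.3 points for the imbalance. A 5-point gap is thus 1.5 standard errors and a 10-point gap 3.0; the latter would take real selection.

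**4. Precision.** Let p be the prevalence of the factor and P = p·r1 + (1 − p)·r0. The share of outcome variance explained is R² = p(1 − p)(r1 − r0)² / [P(1 − P)].
- Previous caesarean, p = 20%, 80% v 25%: P = 0.36, R² = 0.0484/0.2304 = 0.21.
- Previous caesarean, p = 40%, 90% v 20%: P = 0.48, R² = 0.1176/0.2496 = 0.47.

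On the risk-difference scale the standard error is multiplied by √(1 − R²) = 0.89 to 0.73. For the planned logistic coefficient, with no program effect and equal prevalence, it is multiplied by √{P(1 − P) / [p·r1(1 − r1) + (1 − p)·r0(1 − r0)]}. This gives √(0.2304/0.182) = 1.13 and √(0.2496/0.132) = 1.38: it rises. By the same formula the factor is 1.01 to 1.03 for multiples (prevalence 2% to 4%, 70% to 85% v 28%). For prior gestational diabetes it is 1.01 to 1.04 (prevalence 5% to 10%, Composite 1 rate 50% to 70% v 27%).

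**5. Can the models carry the extra terms?** Expected composite events at 30% v 20% are 0.30 × 1200 + 0.20 × 224 = 360 + 44.8, or about 405. A group indicator, five named adjusters and five Table 3 variables make 11 parameters, 404.8/11 = 36.8 events each. Adding all three factors to one model makes 14, or 28.9 each.

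**The case against.** The strongest reply is that the plan does not close its list. The adjusters are given as examples, Table 2 is cited, and adjustment for confounders is promised separately. The rule requires the set to be the same across models; it does not fix what is in it. That stands. A reader might infer that prior gestational diabetes is excluded, but the documents show only that it is not named. The reply does not help the other two factors, which are in no table.

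A common set also has a legitimate purpose: it prevents adjusters from being chosen outcome by outcome after the data are seen. That stands too, and it is why additions should be specified in advance.

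It may be tempting to say that the named set has no bearing on Composite 2. This goes too far: maternal age, diabetes, hypertension and overweight are plausible risk factors for pre-term birth and abnormal fetal growth. A reader might also infer that twins will enter as two dependent rows. Nothing proposes newborn-level rows, and section 15 counts members. The plan is merely silent on how a pregnancy with one affected twin is coded.

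Finally, a reader might expect adjustment for previous caesarean to cut the standard error by 11% to 27%. That holds on the risk-difference scale, but section 3 plans logistic regression, where the standard error of the log odds ratio rises. Power may still improve, because the conditional odds ratio moves away from 1. The R² values are also marginal, so the gain beyond the named adjusters is probably smaller, notably for prior gestational diabetes.

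**Conclusion.** The point holds as a matter of confounding control. As written, every model shares one set, number of fetuses and previous caesarean are in no table, and random selection does not balance them between the 224 women who joined and the comparison group.

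For the primary Composite 2 the effect is small: about 0.4 to 0.6 points per 1-point imbalance in multiples, against a standard error of about 3.3 points. For delivery mode it is larger, about 3 to 7 points for a 5 to 10 point imbalance in previous caesarean, but that outcome is exploratory. All of this rests on assumed prevalences and rates; the documents show no actual imbalance and do not indicate its direction. The change is worth making because it is cheap, not because the primary result is in serious doubt.

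**What to change.** Amend only the sameness rule in section 3, for example:

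> All models share a closed set of pre-exposure covariates: maternal age, gestational age at enrollment, pre-pregnancy diabetes, chronic hypertension, pre-pregnancy overweight/obesity and history of gestational diabetes. Number of fetuses is added for Composite 2, birthweight and cost; previous caesarean is added for delivery mode. Gestational age at delivery is not a covariate in any model. The unit of analysis is the woman, who has a Composite 2 event if any fetus or newborn has one. Composite 2 is repeated in singleton pregnancies.

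Any other Table 2 baseline item that the team intends to use should be named in the same sentence. The clause that carries the dose variables into every model is a separate issue; it should be dealt with openly and not lost in this edit.

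Request number of fetuses and previous caesarean from the health plan now. The data are still to be received, and sections 5 and 17 say that they will be anonymized so that records cannot be linked back, so fields may be hard to add after transfer.

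The cost is two data fields and one or two more parameters per model, which about 405 expected composite events can carry. The main risk is that claims may record previous caesarean incompletely for newly enrolled members. If it is taken from the delivery claim, recording could depend on the delivery mode itself. Completeness should be reported by group and by delivery mode before the adjusted result is relied on.

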Members of the Driscoll Health Plan could be enrolled in the program if they were pregnant and aged 30 years or older at the time of DHP enrollment.

15 **Total Sample Size**

To input text click in the light grey area below.

We expect to receive data from approximately 1700 DHP members broken down as the following (approximate numbers):

- Exposed group: DHP selected 511 members between October 2022 and July 2023, of whom 224 were contacted and opted into the Nurture program.
 - CHWs could not reach the remaining 287 women on the list and, therefore, could not confirm address and book consultations. We will receive the demographic data on this group to explore how they compare with the other two groups in terms of their population descriptors (Table 2 in section 3).
- Comparison group: approximately 1200 women who were 30 years old or older and pregnant during the same enrollment period and were not selected during the DHP's enrollment process.

16 Sample Size Rationale

Provide justification for the sample size and its adequacy for answering the research question.

To input text click in the light grey area below.

Data coming from claims are mostly binary, which is characterized by limited variability and increased uncertainty in proportions. This fact makes detecting statistically significant differences more challenging, requiring larger sample sizes to ensure the reliability of the findings in such studies using these binary outcomes—which is the case of Nurture.

Statistical power is critically dependent on the base rate of the outcome metrics among the comparison subjects. But, when the comparison group is composed of unmatched subjects that is at least four times the size of the exposure group, statistical power tends to be maximized.

That being said, the analysis needs to include all women as described in the previous section.

Because we do not know the incidence rate of the outcomes of interest, we estimated the effect sizes we can capture at 80% power with $\alpha = 0.05$ assuming different rates among comparison subjects (30% and 35%) and four different rates among exposed subjects (25%, 23%, 20%, 18%).

Table 4 demonstrates the statistical power to detect differences between the exposed and comparison groups, assuming *Nurture* produces certain effects. If the composite outcome rate is around 30% among comparison subjects, we have enough power to

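### Composite 1 is counted over the whole pregnancy with no start tied to the programme offer, so diagnoses made before the offer count as outcomes; set a common day 0 at the bi-weekly roster date

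*Combined protocol and SAP*

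**What the plan says.** **Selection.** Section 3, enrollment step 1, says of DHP: "Their data analytics team identified new pregnant members aged 30 or older in bi-weekly" cycles, and that it "ran an algorithm to randomly select a list of names to be notified and contacted". The same step states that "DHP receives daily new health plan enrollees from the TX State".

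**Comparison group.** Section 3 words it as follows: "The women who were covered during the same period but were not selected were not exposed to the program". Section 15 puts it at about 1200 women who were "30 years old or older and pregnant during the same enrollment period and were not selected during the DHP's enrollment process". Neither place gives these women a roster date or index date.

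**Outcome window.** Table 1 heads Composite 1 "Adverse health events during pregnancy". Its components are gestational diabetes, excessive weight gain and pregnancy-associated hypertension. Section 3 defines when participation ends, but gives no matching start for counting outcomes.

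**Adjustment.** Besides maternal age, section 3 names "gestational age at the time of enrollment, pre-existing diabetes, hypertension, and being overweight pre-pregnancy". Table 2 adds family history of diabetes and gestational diabetes in an earlier pregnancy. The plan does not say which enrollment the gestational age refers to: section 14 speaks of enrollment in DHP, while section 3 also uses the word for entry into Nurture.

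**The concern.** A woman may already carry a gestational diabetes or pregnancy-associated hypertension diagnosis when her name is drawn. Under the plan as written she counts as a Composite 1 event, although the programme had no chance to prevent it. The covariates describe disease and history from before this pregnancy, so they do not pick up an event earlier in the same pregnancy. Adjusting for gestational age at enrollment does not remove such an event either.

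If early events are equally common in both groups, they add the same fixed amount to each rate and pull the risk ratio towards 1. Equal frequency is not assured. The draw was random, but the planned contrast is between unselected women and the 224 of 511 (44%) who were reached and agreed. Without a stated index date for comparison women, it is also unclear at what point their gestational age at enrollment would be measured.

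**Working it through.** **Who the comparison women are.** Section 15 expects about 1700 women, of whom 511 were selected. 1700 − 511 = 1189, which agrees with the stated figure of about 1200. This fits a comparison group made up of everyone on the lists who was not drawn. The section 3 wording (covered in the same period) is looser, so the natural reading needs only to be confirmed.

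**Inputs for the illustration.**
- From section 15: 224 exposed and 1200 comparison women.
- From section 16 and Table 4: alpha 0.05, and rates of 30% and 20%. The plan does not state sidedness; I assume two-sided.
- Assumed, because the documents give no diagnosis timing: *s*, the share of comparison-group events dated before day 0, at 5, 10 and 20%; and *f*, the share of early events that claims can flag.
- Assumed: early events are equally common in both groups, and later events are cut by one third, as in the 30% v 20% cell.

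**The plan's own figure.** With pooled rate p̄, power = Φ[(|pc − pe| − 1.96·SE0)/SE1], where SE0 = √[p̄(1 − p̄)(1/224 + 1/1200)] and SE1 = √[pe(1 − pe)/224 + pc(1 − pc)/1200]. For 20% v 30%, p̄ = (224 × 0.20 + 1200 × 0.30)/1424 = 0.284, SE0 = 0.0328 and SE1 = 0.0298. The argument is (0.100 − 0.0643)/0.0298 = 1.20, so power is 88%. Table 4 states 80% without giving its group sizes. The losses below are measured from 88%; the mismatch with Table 4 is a separate matter.

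**With early events.** All women are kept:

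pc = 0.30·s·(1 − f) + 0.30·(1 − s)

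pe = 0.30·s·(1 − f) + 0.20·(1 − s)

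Example: for s = 0.20 and f = 0, pe = 0.06 + 0.16 = 0.22 and pc = 0.30. The risk ratio is 0.73. SE0 = 0.0329 and SE1 = 0.0307, so the argument is (0.080 − 0.0646)/0.0307 = 0.50 and power is 69%.

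| Early share s | All events counted (f = 0) | A quarter flagged (f = 0.25) | All flagged (f = 1) |
|---|---|---|---|
| 5% | 20.5 v 30.0%, ratio 0.68, power 85% | 20.1 v 29.6%, ratio 0.68, power 85% | 19.0 v 28.5%, ratio 0.67, power 86% |
| 10% | 21.0 v 30.0%, ratio 0.70, power 80% | 20.3 v 29.3%, ratio 0.69, power 81% | 18.0 v 27.0%, ratio 0.67, power 83% |
| 20% | 22.0 v 30.0%, ratio 0.73, power 69% | 20.5 v 28.5%, ratio 0.72, power 71% | 16.0 v 24.0%, ratio 0.67, power 77% |

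The last column is a ceiling, because it treats all of Composite 1 as divisible at day 0, and excessive weight gain is not. Even there power stays below 88%, because fewer events are counted.

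If women already diagnosed at day 0 are instead removed from both groups, each group shrinks by the factor 1 − 0.30·s and the later-event rates are divided by the same factor. At s = 10% that is 217 v 1164 women, 18.6 v 27.8%, power 84%. At s = 20% it is 211 v 1128 women, 17.0 v 25.5%, power 78%. The choice between the two rules hardly affects power.

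**The case against.** The other side has four good arguments.

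1. A window is stated: the whole pregnancy, the same for both groups. A reader might infer that Composite 1 has no window, or that exposed women would be counted from the offer and comparison women over the whole pregnancy, which would make an ineffective programme look protective. The documents support neither reading. What is missing is a start tied to the offer.
2. A woman can hardly be passed over in a selection process she was never part of, and 1189 fits about 1200. A reader might infer from section 3 that women never on a list are included. The text does not say so. This half of the point is a request for confirmation.
3. Events before the roster date precede the random draw, so they are balanced in expectation between selected and unselected women. That is correct, but it is not the planned contrast. Any imbalance would come from reach and opt-in. The documents give no information on its direction or size, so no claim about either is made here.
4. The remedy may recover little. If new members means women new to the plan, DHP may hold few claims from before the roster date, and a diagnosis made before joining may first appear afterwards. This stands: with a quarter of early events flagged, the gain in power is under 2 points.

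The roster date also precedes contact and the mailing of packages, so it is not the start of exposure. It is still a sound anchor, because it exists for every listed woman and does not depend on being reached.

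**Conclusion.** The point holds. As written, Composite 1 counts gestational diabetes and pregnancy-associated hypertension diagnosed before the offer, and no rule or covariate deals with them. The main reason to act is validity: an outcome should not predate the exposure it is meant to reflect.

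The size is unknown. Under balanced early shares of 5, 10 or 20%, power falls by about 4, 8 or 19 points from 88%, and a true risk ratio of 0.67 shows as 0.68, 0.70 or 0.73. These figures rest on the assumed shares, on balance, and on a one-third reduction in later events. Only part of the loss can be recovered.

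A reader might infer that a common day 0 would restore the randomised comparison. It would not: the exposed group would still be the women who were reached and opted in.

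**What to change.** - Confirm that comparison women are the unselected women on the same bi-weekly rosters.
- Use the roster date as day 0 for every woman, and define gestational age at enrollment on that date.
- Have DHP derive, before it de-identifies the data (section 5), gestational age at day 0 and a before/after day 0 flag for the first gestational diabetes claim and the first pregnancy-associated hypertension claim.
- Count those two components only after day 0. Apply one stated rule in both groups to women already diagnosed at day 0: either baseline history or exclusion from the at-risk set.
- Report the whole-pregnancy composite as a sensitivity analysis.
- Ask DHP whether its "database and other administrative sources" hold diagnoses made before a woman joined the plan.
- State the limits: excessive weight gain cannot be split by a claim flag and stays whole-pregnancy, so the composite has mixed windows; removal of early events is partial; and selection by reach and opt-in remains.

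**Cost.** A few fields derived by DHP and some protocol wording. Fewer Composite 1 events are counted. If confirming the roster shrinks the comparison group, the loss is small: for 20% v 30%, 1189, 1000 or 800 comparison women give power of 88, 87 or 86%.
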